Name of Sponsor: Gedea Biotech AB
Name of Products: Gedea Pessary (commercial name pHyp)
Name of Active Ingredient: Glucono-delta-lactone (GDL) and sodium gluconate (NaG)
Title of Study: An open-label study to evaluate clinical performance of Gedea Pessary in adult women with bacterial vaginosis (BV).
Clinical Investigation Plan Number: QRS-CL2-003
Investigators and Study Center(s): NAME , VO Kvinnosjukvård, Skånes universitetssjukvård, Lund, Sweden NAME , Stortorgets Gynekologmottagning, Helsingborg, Sweden NAME , MD, Capio Novakliniken Sjöstad, Ystad, Sweden Kliniska prövningssenheten, Kliniska Studier Sverige - Forum Söder, Skånes universitetssjukhus, Lund, Sweden
Classification of Trial: Feasibility Clinical Investigation
Objectives: To investigate the clinical performance, tolerability, and safety of the investigational product.
Methodology: This is an open-label, single-armed, multi-center study to evaluate clinical performance, tolerability, and safety of Gedea Pessary in 24 adult women with confirmed BV according to fulfillment of at least 3 of the 4 Amsel criteria. On Day 0, patients will have gynecological examination, vaginal samples taken, and will receive 4 doses of the investigational product to be self-administered 2 days apart (Day[s] 0, 2, 4, and 6). Patients will be examined after 7 days with respect to 3 Amsel criteria (the criterion: "pH of vaginal fluid above 4.5" is only included at study inclusion for diagnosis), and if not cured, will receive prolonged treatment to be administered on Day(s) 7, 9, 11, and 13. Patients will be followed-up by telephone up to 29 days after last treatment. Vaginal samples will be used for confirming diagnosis and microbiome analyzes. Patient questionnaires will be used for assessing BV symptoms, usability, and adverse events (AEs).
Number of Subjects Planned: Twenty-four (24) patients

Diagnosis and Main Criteria for Inclusion:

Inclusion Criteria:

- Adult, post-menarchal, pre-menopausal women aged 18 years or older
- Diagnosis of BV according to Amsel's criteria, defined as having at least 3 of the 4 following criteria:
 1. Thin, white, yellow, homogenous discharge
 2. Clue cells on microscopy (more than 20 percent of epithelial cells)
 3. pH of vaginal fluid above 4.5
 4. Release of fishy odor "i.e. a positive whiff test" when alkali (10% potassium hydroxide [KOH] solution) is added
- Having decisional capacity and providing written informed consent
- Negative urine pregnancy test at screening
- Refrain from using any intravaginal products (i.e., contraceptive creams, gels, foams, sponges, lubricants, or tampons, etc.) during the study period
- Refrain from sexual intercourse or use a condom until Day 7
- Signed informed consent and willing and able to comply with all study requirements

Exclusion Criteria:

- Patients with known or apparent signs of other infectious causes of BV (vulvovaginal candidiasis, *Trichomonas vaginalis*, *Neisseria gonorrhoeae*, *Chlamydia trachomatis*, *Herpes simplex*, or human papillomavirus) at screening
- Anticipated menstruation during the treatment period (Day 0 till Day 7)
- Patients who are pregnant or breastfeeding
- Patients who were treated for BV within the past 14 days
- Patients who are currently receiving antibiotic therapy unrelated to BV or have received antibiotic therapy within the past 14 days
- Patients who have used pH-modifying vaginal products within the last 14 days
- Patients who have received an investigational drug in a clinical investigation within 30 days prior to screening
- Known/previous allergy or hypersensitivity to any product constituent
- Any medical condition that in the Investigator's judgments would make the patient unsuitable for inclusion

Investigational Product, Dose, and Mode of Administration:

Gedea Pessary, containing 300 mg GDL and 367.5 mg NaG, administered vaginally.

Study Duration:

Up to 5 weeks for each patient, planned first patient in December 2018.

Criteria for Evaluation:

Primary endpoints:

- Clinical cure rate on Day 7.
 - Defined as absence of all of the following 3 Amsel criteria:
 1. Thin, white, yellow, homogenous discharge
 2. Clue cells on microscopy (more than 20% of epithelial cells)

3. Release of fishy odor “i.e. a positive whiff test” when alkali (10% potassium hydroxide [KOH] solution) is added

- Safety and tolerability, based on reported treatment-emergent AEs

Secondary endpoints:

All patients

- Proportion of patients being negative for each of the 3 Amsel criteria on Day 7 compared to Day 0
- Proportion of patients having a reduction in the sum of the 3 BV symptoms scores (fishy smell, burning, and irritation) on Day 4 and Day 7, compared to Day 0
- Change in the sum of the 3 BV symptoms scores (fishy smell, burning, and irritation) from Day 0 to Day 4 and Day 7
- Usability, measured by patient questionnaire

For patients not receiving prolonged treatment

- Recurrence rate on Day 14 and Day 35, defined as the proportion of patients clinically cured on Day 7 and thereafter responding “yes” to a yes/no question from the patient questionnaire on whether the symptoms have recurred

For patients receiving prolonged treatment

- Proportion of patients receiving prolonged treatment
- Clinical cure rate on Day 14, defined as the absence of all of the 3 Amsel criteria as defined above
- Proportion of patients being negative for each of the 3 Amsel criteria on Day 14 compared to Day 0
- Proportion of patients having a reduction in the sum of the 3 BV symptoms scores (fishy smell, burning, and irritation) on Day 11, Day 14, Day 21, and Day 42, compared to Day 0
- Change in the sum of the 3 BV symptoms scores (fishy smell, burning, and irritation) from Day 0 to Day 11, Day 14, Day 21, and Day 42
- Recurrence rate on Day 21 and Day 42, defined as the proportion of patients clinically cured on Day 14 and thereafter responding “yes” to a yes/no question from the patient questionnaire on whether the symptoms have recurred
- Proportion of patients receiving rescue treatment on Day 14

Exploratory endpoint variables:

All patients

- Effect on vaginal microbiome on Day 0 and Day 7
- Vaginal pH on Day 7

For patients not receiving prolonged treatment

- Effect on vaginal microbiome on Day 35

For patients receiving prolonged treatment

- Effect on vaginal microbiome on Day 14 and Day 42

Safety and Tolerability Endpoints:

See above, safety and tolerability, based on reported treatment-emergent AEs.

Statistical Methods:

Sample size (n=24) is based on having 90 % power to show that the one-sided 95 % confidence interval for the observed cure rate is above 40 %, assuming the true clinical cure rate, as defined in this study, to be equal to 70 % in this patient population.

Clinical performance and safety analyses will be performed against the full analysis set (FAS) population, i.e. all patients who have received at least 1 dose of study treatment. The first co-primary endpoint, the clinical cure rate will be calculated and presented together with a one-sided 95 % confidence interval based on the exact binomial distribution, whereas the evaluation of the second co-primary endpoint (safety and tolerability) will be based on descriptive statistics and data listings. The secondary endpoints will be presented with the appropriate point estimate together with the 95% confidence interval, if applicable. Further, all clinical performance and safety endpoints will be presented descriptively.

Clinical Investigation Plan Approval Date:

31OCT2018

TABLE OF CONTENTS

INVESTIGATORS AND STUDY ADMINISTRATIVE STRUCTURE	2
APPROVAL PAGE	5
SYNOPSIS	6
TABLE OF CONTENTS	10
LIST OF ABBREVIATIONS	13
1 INTRODUCTION	14
1.1 Indication	14
1.2 Biofilm and Glucono-Delta-Lactone	15
1.3 Product Description and Previous Experience	15
1.3.1 Non-Clinical Data	15
1.3.2 Clinical Data	16
2 STUDY OBJECTIVES	17
2.1 Primary Objectives	17
2.2 Secondary Objectives	17
3 STUDY DESIGN.....	18
3.1 General outline	18
3.2 Rationale for Study Design.....	20
3.2.1 Risks and Benefits	20
3.3 Recruitment	21
3.4 Schedule of Assessments and Procedures.....	22
3.5 Study Visits and Procedures	24
3.5.1 Day 0; Screening and Enrollment	24
3.5.2 Day 2; Treatment Administration.....	24
3.5.3 Day 4 (+2 Days); Follow-up Telephone Contact	25
3.5.4 Day 6; Treatment Administration.....	25
3.5.5 Day 7 (+2 Days); Follow-up Visit	25
3.5.6 Day 9; Treatment Administration.....	26
3.5.7 Day 11 (+2 Days); Follow-up Telephone Contact	26
3.5.8 Day 13; Treatment Administration.....	26
3.5.9 Day 14 (\pm 2 Days); Follow-up Telephone Contact	26
3.5.10 Day 14 (+2 Days); Follow-up Visit	27
3.5.11 Day 21 (\pm 2 Days); Follow-up Telephone Contact	27
3.5.12 Day 35 (\pm 2 Days); Follow-up Telephone Contact	28
3.5.13 Day 42 (\pm 2 Days); Follow-up Telephone Contact	28
3.6 Early Withdrawal Procedures	28
4 SELECTION OF STUDY POPULATION	29
4.1 Patient Population and Number of Patients.....	29
4.2 Inclusion Criteria	29
4.3 Exclusion Criteria	29
4.4 Withdrawal and Termination Criteria	30
4.5 Reasons for Withdrawal.....	30
4.6 Handling of Withdrawals	30
4.7 Replacements	31
4.8 Sponsor Termination of Study	31

5	TREATMENTS.....	31
5.1	Investigational Product	31
5.1.1	Investigational Product Accountability	32

1 INTRODUCTION

1.1 Indication

Bacterial vaginosis (BV) is the most common cause of foul-smelling vaginal discharge in females of reproductive age. Other symptoms that may be present include vaginal itching or a burning sensation while urinating. It is estimated that BV affects between 10% to 30% of heterosexual women^{1,2} and 20% to 50% of homosexual women.³⁻⁷ The prevalence varies between populations and have been reported to be as high as 50% in parts of Asia and Africa.⁸ Further, it is estimated that BV contributes to over 60% of vulvovaginal infections and may cause preterm delivery, increase the risk of transmission of HIV and other sexually transmitted infections, and lead to increased stress and reduced quality of life.^{9,10} Diagnosing BV clinically usually involves, apart from gynecological examination, vaginal sampling which is tested for fishy odor after addition of a 10% potassium hydroxide (KOH) solution, increased pH (> 4.5), and presence of clue cells. These criteria, including presence of discharge, constitute the Amsel criteria¹¹ and is confirmatory of diagnosis in the majority of cases.¹²

The vaginal microbiome is a dynamic system with a complex mixture of microorganisms in different ratios and quantities, which depend on lactic-acid producing bacteria to maintain a weakly acidic environment, see overview.¹³ Bacterial vaginosis is characterized by a shift in the vaginal microbiota and a high species diversity. There is an increased presence of facultative anaerobes, which leads to a rise in vaginal pH, which can be accompanied by a depletion of *Lactobacillus* species.¹⁴ Up to 50% of patients experience recurrence within 1 year following treatment,⁹ often leading to repeated treatment with antibiotics, which further adds to the issue of antibiotic resistance.¹⁵ The high recurrence rate can be explained by the inability of conventional antibiotics, such as metronidazole, to fully eradicate the biofilm that forms in BV. The polymicrobial microfilm that develops in BV is dominated by *Gardnerella vaginalis*, *Mobiluncus spp.*, *Bacteroides spp.*, *Prevotella spp.* and *Atopobium vaginae*.^{14,16} Biofilms are only temporarily suppressed by antibiotic treatment and rapidly regain activity upon treatment cessation.¹⁶ In addition, vaginal or systemic antibiotics treatment is frequently followed by vulvovaginal candidiasis, likely due to the elimination of the protective bacterial flora, thereby allowing *Candida* overgrowth.¹⁷⁻²¹

Current recommended first-line treatments for BV are oral or topical metronidazole and topical clindamycin.²² Initial cure rates are usually 70% to 80% and recurrence rates are high (Table 1). Metronidazole interacts with many other drugs and concomitant alcohol intake is advised against.²³ The recommended treatment for BV in pregnant women is oral metronidazole or oral clindamycin; topical treatments are not recommended for women at high risk of preterm birth or obstetric complications, due to not having the same effect as oral treatment in preventing BV-associated preterm birth.²⁴ Other antibiotic treatments include oral secnidazole²⁵ and vaginal rifaximin,²⁶ but these are not included as recommended treatments in most clinical guidelines. The U.S. Food & Drug Administration (FDA) approved secnidazole in 2017 for the treatment of BV but it is not approved for use in BV in Europe.

In the absence of effective therapies and in an attempt to treat recurrent symptoms, some women resort to self-treatment remedies, such as oral or vaginal yoghurt, antiseptic creams, over-the-counter (OTC) antimycotics, wearing cotton underwear, and douching. These most often have limited effect, and douching is even associated with a higher incidence of BV.²

Taken together, there remains an unmet medical need for novel treatment and prevention options for patients with BV, especially treatments targeting vaginal biofilms, while allowing beneficial microbes to thrive.

Table 1 Cure Rates and Recurrence of Antibiotic Therapies for Bacterial Vaginosis

Therapy	Duration of Treatment	Clinical Cure Rate (%)	Recurrence Rate	Ref.
Metronidazole, oral	Twice daily, 5-7 days	40-90	>50% within 12 months	9,14,16,24,27
Metronidazole, gel	Once daily, 5 days	30-80	>50% within 12 months	9,14,16,27
Clindamycin, oral	Twice daily, 7 days			
Clindamycin, cream	Once daily, 5 days	33-90	9-30% after 4 weeks. >50% within 12 months	9,14,24,27
Tinidazole, oral	Twice daily, 7 days	70-100	20-40% 2 months after treatment	16,27
Dequalinium, suppository	Once daily, 6 days	81.5		27
Secnidazole*	Single dose	52-68		25
Rifaximin, intravaginal	Not reported	26-46		16

*Phase II Study

1.2 Biofilm and Glucono-Delta-Lactone

It is estimated that approximately 80% of pathogen infections in humans are related to the formation of biofilm, i.e., a complex 3-dimensional structure of pathogens attached to cell walls and to other pathogens. It has been shown that biofilm formation is essential in the pathogenesis of BV, and that presence of biofilm is coupled to treatment failure and recurrent infections.²⁸⁻³² Biofilm formation is dependent both on pH and the availability of alternative carbohydrate sources. The vulvovaginal tract is generally acidic and rich in lactic acid and acetic acid. Interestingly, it has been shown that the addition of gluconic acid strongly diminished the biofilm formation in *Vibrio cholera*.³³ Prokaryotes, such as *V. cholera*, uses gluconic acid as a carbon source using the Entner-Doudoroff pathway. We have shown that glucono-delta-lactone (GDL) can significantly reduce the growth and biofilm formation by *Escherichia coli* to a similar level as lactic acid (see IB for further details), a clinically proven treatment for bacterial vaginosis. In addition, it inhibits growth of *G. vaginalis*. The effect on biofilm formation is not only due to a lowering of the pH, as treatment with GDL inhibits the formation of biofilm even at pH 6. For comparison, biofilm formation was measured at different pH levels in phosphate buffer, with significantly less effect. Furthermore, GDL treatment was found to remove also mature biofilm (biofilm grown for 2 days before treatment, data not shown).

1.3 Product Description and Previous Experience

1.3.1 Non-Clinical Data

Glucono-delta-lactone is a normal intermediate in glucose metabolism through the pentose phosphate cycle in mammals. Animal studies show that GDL gives similar weight increase as

glucose in rats on low-calorie diets.³⁴ Furthermore, several studies on humans have been performed using oral doses between 3 g and 50 g of GDL with no signs of toxicity.³⁵ The investigated studies showed no evidence for carcinogenicity, teratogenicity, or genotoxicity of GDL, nor D-gluconic acid or the magnesium, potassium, calcium, or sodium salts thereof. In addition, both FDA and the World Health Organization International Programme on Chemical Safety (ICPS) accepts GDL as a safe food additive.^{36,37}

In this study, GDL and sodium gluconate (NaG) have been formulated as a slow-release vaginal tablet/ pessary. Sodium gluconate is the sodium salt of the anion of gluconic acid and in a water solute, both GDL and NaG are in equilibrium with gluconic acid. Biological evaluation of the pessary has been performed in accordance with International Organization for Standardization (ISO) 10993 (Biological Evaluation of Medical Devices). The biological evaluation included: cytotoxicity testing (direct cell contact test, ISO 10993-5); *in vivo* irritation (vaginal acute irritation, ISO 10993-10); and sensitization (local lymph node assay, ISO 10993-10). The tests have been performed by Eurofins Medical Device Testing (Munich, Germany) in compliance with the principles of good laboratory practice (GLP). The cytotoxicity test, which is performed *in vitro* as a direct cell contact test, classified the test item as slight to moderate cytotoxic (scale 1-2 on a 3-grade scale). The *in vitro* cytotoxicity test is a prerequisite to continue with the *in vivo* irritation and sensitization studies. In the *in vivo* irritation test, no signs of irritation or necrosis were observed in the macroscopic assessment after treatment with Gedea Pessary. Also, there were no indicators for irritation of the vaginal mucosa in the histopathology assessment. The sensitization test showed no signs of sensitization after treatment with Gedea Pessary. Thus, it can be concluded that the product fulfilled the current biocompatibility requirements for medical devices. For further pre-clinical data, refer to the Investigator's brochure (IB).

1.3.2 Clinical Data

The GDL-and-NaG-containing investigational device, *Gedea Pessary* (commercial name *pHyph*), has not been tested in previous clinical trials. Products containing polymerized lactic acid have comparable properties to Gedea Pessary, as lactic acid and GDL have the same ability to inhibit bacterial biofilm formation and lower the pH to a similar extent, see IB. One such product, *Laccure Pessary* (Laccure AB, Helsingborg, Sweden), is buffered to pH 3.5, whereas Gedea Pessary is buffered to pH 3.6. Laccure Pessary has been tested in a clinical trial of 126 patients with confirmed BV, where 93 patients were treated with 1 or 2 doses of Laccure Pessary and 33 patients formed the control group.³⁸ The study showed an 80% cure rate for the single-dose treatment. Most adverse events (AEs) reported were of mild intensity and brief. The most common event was vaginal itching, experienced less than 20% of patients. No serious adverse events (SAEs) occurred and the treatment had no visually detectable negative impact on the vaginal mucosa.

Based on published studies on current treatments for BV, oral, topical, and intravaginal antibiotics are generally well tolerated; reported AEs include nausea, headache, diarrhea, vaginal discharge, and vulvovaginal pruritus. The reported frequencies of AEs after treatment with antibiotics are between 4.6% to 42%, depending on antibiotic used and route of administration.^{16,25,27,39}

Collectively, pre-clinical data indicate that GDL and NaG are safe and may be an effective topical treatment for BV, and a GDL-and-NaG-containing slow-release pessary is to be investigated in this clinical trial.

2 STUDY OBJECTIVES

2.1 Primary Objectives

To investigate the clinical performance, tolerability, and safety of the investigational product.

Primary endpoints:

- Clinical cure rate on Day 7
 - Defined as absence of all of the following Amsel criteria:
 1. Thin, white, yellow, homogenous discharge
 2. Clue cells on microscopy (more than 20% of epithelial cells)
 3. Release of fishy odor “i.e. a positive whiff test” when alkali (10% potassium hydroxide [KOH] solution) is added
- Safety and tolerability, based on reported treatment-emergent AEs

2.2 Secondary Objectives

To further investigate the clinical performance of the investigational product.

Secondary endpoints:

All patients

- Proportion of patients being negative for each of the 3 Amsel criterion on Day 7 compared to Day 0
- Proportion of patients having a reduction in the sum of the 3 BV symptoms scores (fishy smell, burning, and irritation) on Day 4 and Day 7, compared to Day 0
- Change in the sum of the 3 BV symptoms scores (fishy smell, burning, and irritation) from Day 0 to Day 4 and Day 7
- Usability, measured by patient questionnaire

For patients not receiving prolonged treatment

- Recurrence rate on Day 14 and Day 35, defined as the proportion of patients clinically cured on Day 7 and thereafter responding “yes” to a yes/no question from the patient questionnaire on whether the symptoms have recurred

For patients receiving prolonged treatment

- Proportion of patients receiving prolonged treatment
- Clinical cure rate on Day 14, defined as the absence of all of the 3 Amsel criteria as defined above
- Proportion of patients being negative for each of the 3 Amsel criterion on Day 14 compared to Day 0
- Proportion of patients having a reduction in the sum of the 3 BV symptoms scores (fishy smell, burning, and irritation) on Day 11, Day 14, Day 21, and Day 42, compared to Day 0
- Change in the sum of the 3 BV symptoms scores (fishy smell, burning, and irritation) from Day 0 to Day 11, Day 14, Day 21, and Day 42

- Recurrence rate on Day 21 and Day 42, defined as the proportion of patients clinically cured on Day 14 and thereafter responding “yes” to a yes/no question from the patient questionnaire on whether the symptoms have recurred
- Proportion of patients receiving rescue treatment on Day 14

Exploratory endpoint variables:

All patients

- Effect on vaginal microbiome on Day 0 and Day 7
- Vaginal pH on Day 7

For patients not receiving prolonged treatment

- Effect on vaginal microbiome on Day 35

For patients receiving prolonged treatment

[figure not shown]
- Effect on vaginal microbiome on Day 14 and Day 42

3 STUDY DESIGN

3.1 General outline

This is an open-label, single-armed, multi-center study to evaluate clinical performance, tolerability, and safety of Gedea Pessary in 24 adult women with BV. Patients seeking treatment can be screened for study participation. Included patients will have gynecological examination, including collection of vaginal samples, and will receive the investigational product to be self-administered at Day(s) 0, 2, 4, and 6. Patients will again be examined after 7 days. Prolonged treatment at Day(s) 7, 9, 11, and 13 will be given to patients not cured at Day 7; including re-examination at Day 14. Patients will be followed up by telephone up to 29 days after last treatment administration. Gynecological examinations include collection of Amsel criteria. Vaginal samples will be used for confirming diagnosis and microbiome analyzes. Patient questionnaires will be used for assessing BV symptoms, usability, and AEs.

Figure 1 Study Flow Chart

AC = Amsel's Criteria, BVS = Bacterial Vaginosis Symptoms, VS = Vaginal Swab (*Self-swab at home)

Patients not receiving prolonged treatment applies to patients cured at Day 7. If not cured, the flow chart *patients receiving prolonged treatment* applies. Patients will here receive an antibiotic if not cured at Day 14. Adverse events will be assessed throughout the study.

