3.5.11 Day 21 (± 2 Days); Follow-up Telephone Contact

Applicable to patients receiving prolonged treatment

Patients receiving prolonged treatment on Day 7 will be contacted by the Clinical Trial Unit by telephone on Day 21. Patients will be asked questions from the patient questionnaire pertaining to BV symptoms (fishy smell, irritation, and burning). Questions on concomitant medications, recurrence, and AEs, if any, will also be asked.

Procedures performed:

- Bacterial vaginosis recurrence
- Symptoms of BV (fishy smell, irritation, and burning) evaluated by patients according to a scoring scale (0-3)
- Recording of:
 - concomitant medications, and
 - adverse events

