3.5.13 Day 42 (± 2 Days); Follow-up Telephone Contact

Applicable to patients receiving prolonged treatment

Patients receiving prolonged treatment will be contacted over telephone by the Clinical Trial Unit on Day 42 and asked questions from the patient questionnaire relating to BV symptoms (fishy smell, irritation, and burning). Patients will also be asked questions on recurrence, concomitant medications, and AEs, if any. Patients will collect vaginal samples by self-swab to be sent by post to laboratory for sequencing.

Procedures performed:

- Bacterial vaginosis recurrence
- Symptoms of BV (fishy smell, irritation, and burning) evaluated by patients according to a scoring scale (0-3)
- Vaginal swab for sequencing
- Recording of:
 - concomitant medications, and
 - adverse events

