3.6 Early Withdrawal Procedures

See [Section 4.6](#) for withdrawal procedures. Patients refusing to visit the site for follow-up visits shall be contacted by telephone, if possible, to collect answers to the patient questionnaire, and AEs, if any. Patients receiving an antibiotic on Day 14 will be followed up for safety assessments.

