6 CLINICAL PERFORMANCE

6.1 Clinical Performance Assessments

Assessments described below in [Section 6.1.1](#), gynecological examination, will be used to diagnose BV according to the following Amsel criteria:

1. Thin, white, yellow, homogenous discharge
2. Clue cells on microscopy (more than 20% of epithelial cells)
3. pH of vaginal fluid above 4.5
4. Release of fishy odor “i.e. a positive whiff test” when alkali (10% potassium hydroxide [KOH] solution) is added

Presence of 3 out of the 4 Amsel criteria above will serve as diagnosis of BV

Clinical cure is defined as absence of the following 3 Amsel criteria and is a primary study endpoint together with safety and tolerability evaluations:

1. Thin, white, yellow, homogenous discharge
2. Clue cells on microscopy (20% of epithelial cells)
3. Release of fishy odor “i.e. a positive whiff test” when alkali (10% potassium hydroxide [KOH] solution) is added

The Amsel score will also be used for the following secondary endpoints:

- Proportion of patients being negative for each of the 3 Amsel criteria on Day 7 compared to Day 0
- Recurrence rate on Day 14 and Day 35, defined as the proportion of patients clinically cured on Day 7 and thereafter responding “yes” to a yes/no question from the patient questionnaire on whether the symptoms have recurred
- Proportion of patients receiving prolonged treatment
- Clinical cure rate on Day 14, defined as the absence of all of the 3 Amsel criteria as defined above
- Proportion of patients being negative for each of the 3 Amsel criteria on Day 14 compared to Day 0
- Recurrence rate on Day 21 and Day 42, defined as the proportion of patients clinically cured on Day 14 and thereafter responding “yes” to a yes/no question from the patient questionnaire on whether the symptoms have recurred
- Proportion of patients receiving rescue treatment on Day 14

Assessments described in [Section 6.1.2](#), patient questionnaire, will be used to assess the following secondary endpoints:

- Proportion of patients having a reduction in the sum of the 3 BV symptoms scores (fishy smell, burning, irritation) on Day 4 and Day 7, compared to Day 0
- Proportion of patients having a reduction in the sum of the 3 BV symptoms scores (fishy smell, burning, irritation) on Day 11, Day 14, Day 21, and Day 42, compared to Day 0
- Change in the sum of the 3 BV symptoms scores (fishy smell, burning, and irritation) from Day 0 to Day 4 and Day 7

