7.2 Clinical Laboratory Evaluation

Vaginal samples will be collected by vaginal swab on Day(s) 0 and 7 (and Day 14 if receiving prolonged treatment) by the Investigator and on Day 35 (or Day 42 if receiving prolonged treatment) by patients. Collected samples will be used accordingly:

- Samples collected on Day 0 will be sent to laboratory and cultured to confirm the BV diagnosis. Time for lab results is approximately 1 week.
- Samples collected on Day(s) 0, 7, 14, and 35 or 42 will be analyzed to assess the effects of the investigational product on the vaginal microbiome before treatment, after the treatment series, and at study end. Collected samples will be sent to laboratory sequencing present bacterial DNA content for complete species overview.

Patients' vaginal pH will be measured for assessments of investigational product *in vivo* duration on Day(s) 0 and 7. Vaginal pH lower at Day 7 compared to Day 0 indicate appropriate release duration.

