3.2 Secondary objectives

To further investigate the clinical performance of the investigational product.

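### The SAP has no rule for symptom scores taken after a Day 14 rescue antibiotic, so at Days 21 and 42 an antibiotic response can count as pessary performance

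*Protocol*

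**What the plan says.** **Rescue.** Protocol 3.1 and SAP 4 describe the prolonged-treatment path in the same words: "Patients will here receive an antibiotic if not cured at Day 14". Protocol 6.1 and SAP 6.1 place Day 14 rescue in a list introduced by "The Amsel score will also be used for the following secondary endpoints". Protocol 3.2.1, 3.5.10 and 5.2.1 are softer: the antibiotic is offered, or given if symptoms remain, or prescribed if judged necessary for symptom relief.

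**Scoring after rescue.** Protocol 3.5.11: "Patients receiving prolonged treatment on Day 7 will be contacted by the Clinical Trial Unit by telephone on Day 21". Protocol 3.5.13: "Patients receiving prolonged treatment will be contacted over telephone by the Clinical Trial Unit on Day 42". Both contacts include the symptom score, Table 3 agrees, and none of the three makes an exception for women who took an antibiotic. Protocol 3.6 adds: "Patients receiving an antibiotic on Day 14 will be followed up for safety assessments". It does not say whether symptom scoring stops.

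**Analysis.** The secondary objective (SAP 3.2) is "To further investigate the clinical performance of the investigational product". Under it, SAP 7.9.2 analyses Days 21 and 42 in prolonged-treatment women:
- Endpoint ix is the proportion with a reduced symptom sum, with an exact two-sided 95% interval and no test.
- Endpoint x is the mean change in the sum, with a t interval and a two-sided null hypothesis of zero change.

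SAP 7.1.5 uses observed data without imputation. SAP 8.4 and 8.7 define change and reduction without mentioning rescue. Rescue use is flagged (SAP 7.7), reported as endpoint xii and listed with dates (SAP 8.10). It is not linked to ix or x.

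**The concern.** A woman whom the pessary has not cured can take an antibiotic on Day 14, improve because of it, and be counted on Days 21 and 42 as improved under a pessary endpoint. With no comparator, nothing in the analysis separates the two effects. The worse the second pessary course performs, the more women become eligible for rescue, so the later results are flattered most when the product does least.

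The alternative reading of protocol 3.6, safety-only follow-up after rescue, brings a different problem. Rescued women's scores would be missing, and the two endpoints would treat the same women differently.

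**Working it through.** The plan gives no figure for rescue or for the Day 21/42 scores, so there is none to reproduce. The figures below illustrate the size.

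**Inputs from the documents.** 24 women and a 70% Day 7 cure rate (protocol 9.3, SAP 5.1). Antibiotic cure: "Initial cure rates are usually 70% to 80% and recurrence rates are high" (protocol 1.1); Table 1 is wider, for example 30-80% for metronidazole gel. Each symptom is scored 0-3, so the sum runs from 0 to 9.

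**Assumptions.** Day 14 cure rate, share of uncured women prescribed, size and SD of score changes, and a baseline sum of 5.

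**1. How many women.**
- Prolonged: 24 × 0.30 = 7.2 (5th to 95th binomial percentile 4 to 11).
- Rescued if every uncured woman is prescribed: 24 × 0.30 × 0.30 = 2.2 at 70% Day 14 cure, and 24 × 0.30 × 0.60 = 4.3 at 40%. P(at least one) = 1 − 0.91^24 = 89.6% and 1 − 0.82^24 = 99.1%.
- If half are prescribed: 1.1 and 2.2 women. P(at least one) = 1 − 0.955^24 = 66.9% and 1 − 0.91^24 = 89.6%.

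**2. One example under three readings.** Seven women: 3 cured on Day 14 with a change of −3, and 4 rescued with no change before the antibiotic, of whom 3 then respond with −3.

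| Reading | ix (exact 95% CI) | x, mean change |
|---|---|---|
| Observed scores used after rescue | 6/7 = 85.7% (42.1 to 99.6) | (6 × −3)/7 = −2.6 |
| Safety-only follow-up, scores missing | 3/7 = 42.9% (9.9 to 81.6), by the SAP 7.1.1 denominator | (3 × −3)/3 = −3.0, cured women only |
| Scores before the antibiotic | 3/7 = 42.9% (9.9 to 81.6) | (3 × −3)/7 = −1.3 |

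**3. Chance that the test of x shows benefit.** Simulation, 40,000 runs per cell: 7 women, integer scores kept within 0-9, 3-point fall when BV clears, one-sample two-sided 5% t-test, benefit counted when t lies below its 2.5% quantile. Ranges cover SD 1 to 1.5. Unless stated, antibiotic cure is 75%, every uncured woman is prescribed, and uncured women do not change without the antibiotic.

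| Scenario | Without antibiotic effect | With post-antibiotic scores |
|---|---|---|
| Day 14 cure 0% | 3% | 69-81% |
| 0%, half prescribed | 3% | 20-24% |
| 0%, antibiotic cure 50% | 3% | 34-41% |
| 0%, antibiotic cure 30% | 3% | 14-16% |
| Day 14 cure 40% | 22-27% | 83-92% |
| 40%, half prescribed | 22-27% | 50-61% |
| Day 14 cure 70% | 61-73% | 92-98% |
| 0%, uncured women improve by 1 point | 32-60% | 87-97% |
| 0%, uncured women improve by 2 points | 83-99% | 97-100% |

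The last two rows matter because x is measured from Day 0, so improvement during the first course also counts.

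**The case against.** **Rescue is discretionary.** Protocol 5.2.1, the dedicated section, ties the prescription to need. Cure requires absence of all three criteria, so a woman with only residual discharge is uncured but may need no antibiotic. This stands. A reader might infer from protocol 3.1 that every uncured woman is treated, but the documents taken together do not settle that. It changes how many women are affected; the rule is missing either way.

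**Protocol 3.6 may end performance follow-up.** The sentence sits under early withdrawal, and protocol 5.7 otherwise bans antibiotics. On that reading no post-antibiotic score enters, and ix already comes out as the fix would have it. This also stands as a possible reading. But protocol 3.5.11, 3.5.13 and Table 3 schedule the scores without exception, and under safety-only follow-up x would rest on unrescued women alone.

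**The test of x never isolates the pessary.** A single-arm comparison with zero also absorbs natural course and regression to the mean. True, but the antibiotic is a known, dated addition that the analysis can set apart.

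**Other safeguards.** The per-protocol analysis in SAP 7.9 covers only the primary endpoint. The protocol 9 promise to limit bias concerns missing data and outliers, and a post-rescue score is neither.

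**The Day 42 microbiome.** A reader might extend the point to the swabs, since protocol 7.2 describes samples as "analyzed to assess the effects of the investigational product on the vaginal microbiome before treatment, after the treatment series, and at study end". SAP 7.9.3 sets out no analysis for them, so there is no planned result to correct.

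**Conclusion.** The concern holds as a minor omission. As written, the plan lets scores taken after a rescue antibiotic enter Days 21 and 42 of endpoints ix and x as pessary performance. If protocol 3.6 means safety-only follow-up, ix and x instead handle rescued women inconsistently. The plan does not say which applies.

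If the antibiotic works, the direction favours the pessary. The size is uncertain: with 7 women and no cure by Day 14, the chance that x shows benefit goes from about 3% to roughly 14-80%, depending on the share prescribed and the antibiotic cure rate. A reader might take the top of that range as the expected false-positive rate. The documents do not support this, because it needs full prescribing, 75% antibiotic cure and no improvement from Day 0 in uncured women. If those women have already improved by 2 points, the test is positive in 83-99% of runs without any antibiotic.

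Nor does the point reach the trial's main conclusion. The Day 7 primary endpoint and all results up to Day 14 are unaffected, since the Day 14 score belongs to the visit at which rescue is prescribed. Recurrence endpoint xi is restricted in SAP 7.9.2 to women cured on Day 14, so it is largely protected.

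**What to change.** 1. **SAP 8.7, endpoint ix:** count a woman who started a rescue antibiotic before the Day 21 or Day 42 score as not reduced at that visit.
2. **SAP 7.9.2 and 8.4, endpoint x:** at Days 21 and 42 present results split by rescue yes/no, and state that the pooled test against zero is not interpreted as pessary performance. Carrying the Day 14 score forward is single imputation, which SAP 7.1.5 does not plan, so it belongs at most in an optional sensitivity analysis.
3. **Protocol 3.6:** state whether symptom scores continue after rescue.

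The cost is a few sentences and one table split. Day 14 scores and rescue dates are already collected, so no new data or patients are needed. The downside is less favourable ix figures and very small groups in the split: about 7 prolonged women, of whom roughly 1 to 4 would be rescued under the assumptions above.
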